For the patients in the Intervention group, the total individual duration spent by the health counsellor and the investigator, for scheduled and unscheduled actions, separately, will be multiplied by the hourly national health care professional income, as fixed by the National Health System tariffs in force, at the end of the study.

### **6.C.2 Cost-effectiveness**

The cost-effectiveness evaluation performed will relate the estimated difference in costs between both COPD management programs in the perspective of the health care payer to a difference in medical outcome over the 12-month *Follow-Up Period*. The medical outcomes which will be taken into account in this evaluation will be:

- the number of unscheduled hospital days whatever the reason for hospitalisation (*i.e., the primary efficacy criterion defined in section 6.A.1*),
- the number of deaths.

### **6.C.3 Cost-utility**

An incremental cost per Quality-Adjusted Life Year (QALY) gained will be estimated by calculating the ratio between the incremental cost of the Intervention group (*receiving the Home-Based Disease Management Program*) and the Control group (*receiving the usual COPD education and follow-up of their investigational centre*) and the incremental utility.

The incremental cost will be estimated by calculating the difference between the average total costs per patient (*from the date of Visit 1 (included) onwards*) in both study groups.

Incremental utility will be estimated by using the self-evaluations of the 15D health-related quality of life instrument and the Finnish scoring algorithm. QALY weights will be calculated for each six-month study period, and they will be applied to the time period lived throughout the 12-month *Follow-Up Period*.

QALYs per patient in both study groups will be compared and, if relevant, related to the additional incremental cost required to produce one additional QALY (*incremental cost-utility analysis, as detailed in section 7.B.3.6*).

## **6.D ENDPOINT VALIDATION COMMITTEE**

An Endpoint Validation Committee (EVC) will be established to review in a blind manner all hospitalisations having been reported for each randomised patient during the *Follow-Up Period*. The major reason is that hospitalisation may be considered as a potentially biased outcome measure, because somewhat subjective, and physician- or centre-dependent, as health care availability, each physician's routine practice and social considerations can markedly influence the decision to hospitalise a patient.

The EVC will be composed of three (3) independent physicians with clinical and research expertise in COPD. The 3 members will be appointed by the sponsor (AIR LIQUIDE Santé INTERNATIONAL) but will not be involved in the study conduct.

The role of the EVC members will be to adjudicate the reason and appropriateness of all hospital admissions and, for hospitalisations due to COPD exacerbation, to check for the presence of recognised criteria for hospital admission as published in the GOLD 2008 guidelines. Adjudication rules will be defined by the EVC members and sponsor representatives before starting adjudication of cases.

To adjudicate all hospitalisations recorded, the EVC members will review all individual medical reports (*anonymous reports, blinded for study group allocation, and translated in English by the study Clinical Research Associates (CRAs)*) related to hospitalisations having occurred in randomised patients during the *Follow-Up Period*. The following will be adjudicated:

- Criteria for hospitalisation,
- Reason for hospitalisation: first attributing the hospitalisation to a specific cause, then distinguishing hospitalisations directly related to COPD and to other causes, then grouping them into general pathophysiological categories (*respiratory, cardiovascular, cancer or other*),
- Cause of prolonged hospitalisation (*defined by an overall duration of hospitalisation > 30 days*).

Each EVC member will independently analyse, by batches of 50 cases, all hospitalisation reports and will provide the sponsor with a written signed adjudication form for each of them. Cases will be considered as resolved if the 3 members agreed on adjudication parameters. Regular telephone meetings will take place during the study and will be organised to discuss only the reports not unanimously adjudicated in order to further review (*additional medical information could be requested to the investigational centre*) and discuss the case until complete consensus is achieved. Consensus will be written into a final dated and signed adjudication form. All forms and subsequent analyses will be used by the sponsor as supportive information to discuss and interpret the study results. Indeed, whatever the conclusions of the EVC members on the definition of the primary efficacy criterion, the information recorded by the investigators will be used for the primary analysis of the primary efficacy criterion.

## 6.E STUDY FLOW CHART OF EXAMINATIONS AND EVALUATIONS

Examinations and Evaluations	Selection	Run-In	Follow-Up			
	Visit 0	Visit 1*	Visit 2	Visit 3	Visit 4	Visit 5
	Minus 5 weeks	Day 0	Month 3	Month 6	Month 9	Month 12
Informed consent	X					
Demographics – child-bearing potential	X					
Medical and surgical history	X					
Physical examination, vital signs and pulse oximetry, weight ( and height at Selection )	X	X	X	X	X	X
Smoking status assessment	X	X	X	X	X	X
Concomitant medication, including vaccines, oxygen therapy , home ventilation and CPAP, if applicable	X	X	X	X	X	X
Social conditions assessment	X	X	X	X	X	X
Inclusion and Exclusion criteria including ( but not limited to ): - Quantification of airflow obstruction - At least 1 hospitalisation for exacerbation in the year before selection	X X(a) X					
Randomisation	X					
Medical evaluations: Post-bronchodilator pulmonary function tests, six minute-walk test, transthoracic Doppler echocardiography and 12-lead supine resting ECG		X(b)				X(c)
Laboratory tests: Arterial/capillary blood gases on room air (including HbCO), haemoglobin, haematocrit and CRP		X(b)				X(c)
Questionnaires SGRQ-C, 15D and HADS		X(d)		X(d)		X(d)
Train and dispense the NOWOX device, if applicable		X	X	X	X	
Assessment of dyspnoea ( MMRC dyspnoea scale ) and of comorbidities ( Charlson comorbidity index )		X				X
Report COPD exacerbations and use of health care services		X	X	X	X	X
Adverse events		X	X	X	X	X
Collect the NOWOX and other study medical devices, if applicable						X

[figure not shown]
\* Exceptionally, in the event of a medical problem which is expected to be resolved within 4 weeks (*e.g., a COPD exacerbation*) or in case clinical stability is not reached after hospital discharge, the time interval between Visit 0 and Visit 1 may be prolonged by a maximum of 4 supplemental weeks.

(a) Assessed by pulmonary function tests performed less than 12 months prior to Visit 0.

**(b) Tests performed within 3 months before selection can be reported.**

(c) To be performed in the timeframe between this visit and the previous Visit.

(d) To be self-administered before the consultation with the investigator.

## 7. STATISTICAL ANALYSIS

---

### 7.A DATA COLLECTION

An electronic data capture system will be used for this study. The electronic Case Report Forms (e-CRF) used will be designed to record all data related to the study which are to be recorded by the investigators and the health counsellors. Laboratory results and their normal ranges will be entered into the e-CRF by the investigators.

Patients' self-evaluations will be collected in paper format and double-entered into the trial database by data entry operators. Electronic data exported from the *NOWOX* device and from the dedicated vocal server which are not transcribed in the e-CRF will be transferred electronically into the trial database.

During the study, the electronic Case Report Forms (e-CRF) for all participating patients will be filled in by the health counsellors and the investigators *via* Internet and they will be reviewed by the Clinical Research Associates (CRA) on a regular basis. Each investigator and health counsellor will receive a Personal Identification Number and password to connect personally to the e-CRF. The investigators, health counsellors, CRA, data manager and authorised persons will all have individual documented personal access to the e-CRF data, with specific restricted rights depending on their function in the study conduct (*for example, read access only for CRA, medical signature only dispensed to investigators, ...*). The e-CRF will be designed by Lincoln in compliance with the protocol specifications, under the supervision of AIR LIQUIDE Santé INTERNATIONAL.

Data entry at the investigational centre will be performed for each patients visit by the investigator or the designated person from his/her team, using the e-CRF screens specifically designed for the study.

Upon their entry, data will be transmitted *via* Internet from the investigational centre to the trial database. A computerised data review will be performed. Checks for missing data, out of ranges data and consistency will be carried out, according to a pre-specified consistency checks book. Whenever required, electronic queries with deferred corrections will be issued in the e-CRF to the investigator for resolution and electronic signature, and they will be tracked until corrections are entered in the trial database and validated.

All data corrections in the e-CRF must be made by the investigator or the designated person from his/her team using electronic data clarifications according to the provided instructions. All data modification will be recorded in chronological order using the audit trail feature of the e-CRF, including the identity of their author, date and reason for modification.

After the last visit of each patient, when the last queries have been answered, the investigator must attest by entering his/her Personal Identification Number and password, both:

- the authenticity of the data collected in the e-CRF of the given patient,
- and the consistency between the data entered in the e-CRF and those recorded in the corresponding source documents, with the exception of data directly reported in the e-CRF which are considered source data.

Adverse events, concomitant diseases, as well as medical and surgical histories will be coded using the current MedDRA version, while concomitant medication will be coded using the current WHO-DRUG dictionary version.

AIR LIQUIDE *Santé* INTERNATIONAL or any company appointed by the latter will be responsible for the storage of data.

A copy of the original e-CRF data will be kept by the investigator at the end of the study to store them as the current GCP guidelines recommend it.

At the end of the study, the validated database will be locked upon request of AIR LIQUIDE *Santé* INTERNATIONAL following the completion of all steps required, *i.e.*, resolution of all queries, Clinical and Pharmacovigilance databases reconciliation (*for all Serious Adverse Events entered in the Pharmacovigilance database*), and medical and statistical review by the sponsor study personnel (*see section 4.B.4*).

Moreover, once all patients have performed their *Run-In Period* and their data recorded at Visit 0 and Visit 1 have been validated, a preliminary partial database lock will be performed and the description at Selection and during the *Run-In Period* as detailed in section 7.B.3.2 will be performed globally, whatever the study group allocated on the Intention To Treat (ITT) data set defined in section 7.B.3.1.

## 7.B STATISTICAL METHODS

The primary analysis of the primary efficacy criterion is detailed in section 7.B.3.5. All other efficacy, safety and medico-economic statistical results provided will be exploratory and exclusively descriptive. They may not lead to any causal interpretation. As a consequence, the statistical significance level of the various two-sided tests performed will be 5.0%. No adjustment for multiplicity will be made.

At the end of the study, after the database lock, the statistical analysis will be performed by ITEC Services under the supervision of AIR LIQUIDE *Santé* INTERNATIONAL using the current version of the SAS® software, according to the statistical analysis plan approved after the medical and statistical review performed by the sponsor study personnel (*see section 4.B.4*).

Thorough description of all parameters reported will be presented separately by study group (*defined by the education program allocated to the patient at random, i.e., either the Intervention group or the Control group*), using the observed case approach. Summary tabulated results will be provided by study group and assessment time, if relevant or they will be replaced by the corresponding individual data listings if too few patients are concerned.

Quantitative parameters will be described using the following statistics: number of patients, mean, standard deviation, minimum, median and maximum values. Qualitative parameters will be described using frequencies and percentages and for binary variables, by their two-sided 95.0% confidence intervals of the observed rates (*assumed to be binomially distributed in both study groups*).

### 7.B.1 Evaluation parameters

The efficacy criteria will be recorded by the investigators as described in section 6.A. Their analysis is described in section 7.B.3.5.

The primary efficacy criterion will be the number of unscheduled hospital days whatever the reason for hospitalisation as defined in section 6.A.1.

The secondary efficacy criteria defined in section 6.A.2 include the number of hospital days due to severe COPD exacerbations, the number of moderate and severe COPD exacerbations, the use of health care services due to COPD and to all causes, the health-related quality of life, physiological parameters, the BODE index, the Hospital Anxiety and Depression Scale (HADS), the evaluation of compliance to oxygen therapy and respiration rate as recorded by the *NOWOX* device (*in the subgroup of patients on oxygen therapy at Selection and/or during their study participation*), as well as changes in smoking status.

The safety criteria detailed in section 6.B include clinical and laboratory parameters, as well as Adverse Events. Their evaluation throughout the study period is described in section 7.B.3.7.

The medico-economic criteria defined in section 6.C include the estimates of the overall costs from the perspective of the health care payer, as well as cost-effectiveness and cost-utility. Their evaluation is described in section 7.B.3.6.

### **7.B.2**     *Determination of sample size*

The primary objective of this phase IV study is to show that the set-up of the Home-Based Disease Management Program in patients with GOLD III/IV COPD reduces the individual yearly duration of unscheduled hospitalisations whatever their reason. Based on published results and assuming:

- an expected difference of 10 days of hospitalisation between the average individual yearly duration of unscheduled hospitalisation whatever their reason observed in the Intervention group and in the Control group,
- an estimated common standard deviation of 25 days,
- a type I error set to  $\alpha = 0.05$  (*two-sided conditions*),
- and  $(1-\beta)$  power equal to 0.90,

and using the nQuery Advisor® software Version 6.01 and the estimation provided for the Wilcoxon (*Mann-Whitney*) rank-sum test for a continuous outcome, the number of patients required is estimated to be 143 per study group.

With an expected 25.0% dropout rate per year over the *Follow-Up Period* (*i.e., at most 6.25% over the first 3 months (between Visit 1 and Visit 2) with no available individual data allowing the estimation of the primary efficacy criterion (as detailed in section 7.B.3.5) for the concerned patients*), this sample size estimation results in randomising around 306 patients, *i.e.,* approximately 153 patients in the Intervention group and 153 patients in the Control group.

### **7.B.3**     *Statistical methodology*

#### **7.B.3.1.**   Data sets analysed

Two (2) different analysis data sets are foreseen. They will be exhaustively defined prior to the database lock (*see section 4.B.4*):

- Full Analysis data Set (*FAS or extended safety data set*), composed of all randomised patients having entered the *Run-In Period (starting at Visit 0, as defined in section 4.B.3.1)*. This FAS will be used for description of dropouts, and extended evaluation of safety,
- Intention To Treat (ITT) data set, which will be the subset of the FAS, composed of all randomised patients having entered the *Follow-Up Period (starting at the end of Visit 1, as defined in section 4.B.3.2)*. This ITT data set will be used for description at Selection, and evaluation of efficacy, safety and medico-economic parameters.

If prior to the database lock (*see section 7.A*), it appears necessary to define a secondary Per Protocol (PP) data set, which would be a subset of the ITT data set, composed of all randomised patients who have no major protocol deviations throughout their study period, this PP data set would be used for the secondary supportive analysis of the primary efficacy criterion and check of its robustness. For example, if it appears that 25.0% or more of the patients from the ITT data set have prematurely discontinued their allocated COPD management strategy and completed the study as initially planned (*as described in section 3.D*), a secondary supportive analysis of the primary efficacy criterion would be added comparing the recorded average yearly duration of unscheduled hospitalisations whatever their reason, between three (3) groups: *i*) patients from the Intervention group having completed the study as planned, *ii*) patients from the Intervention group having prematurely discontinued the evaluated Home-Based Disease Management Program without being prematurely withdrawn from the study and *iii*) patients from the Control group.

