#### **4.B.5 Study premature withdrawals**

If at any time the study procedures are considered compromised, the concerned patient may be withdrawn from the study at the investigator's discretion. Moreover, patients are free to discontinue their participation in the study at any time as described in their Informed Consent.

The reason and date of study premature withdrawal will be recorded in the e-CRF of the patients concerned (*e.g., consent withdrawn, death, etc...*) by the investigator. As mentioned in section 3.D, patients who are prematurely withdrawn from the study during the *Follow-Up Period* will not be replaced.

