#### 7.B.3.4. Evaluation of protocol deviations

Prior to the database lock, all protocol deviations encountered throughout the study will be reviewed (*see section 4.B.4*) and their consequences on the efficacy evaluations performed will be evaluated. A deviation will be considered major when it is likely to bias significantly the interpretation of the efficacy results, especially the primary efficacy criterion (*i.e., the individual yearly duration of unscheduled hospitalisations whatever their reason*). All other protocol deviations will be considered minor.

A listing of all protocol deviations will be provided for all randomised patients (*i.e., on the FAS defined in section 7.B.3.1*), including the type (*major/minor*) of protocol deviations according to the decisions made. The number and percentage of patients with protocol deviations will be tabulated by study group (*and globally*) and type of protocol deviations on the Intention To Treat (ITT) data set (*defined in section 7.B.3.1*).

Protocol deviations which will be evaluated will include:

- deviations in inclusion and exclusion criteria,
- deviations in dates of visits and assessments times, including the cases of study premature withdrawals,
- deviations in the allocation and/or the performance of the study educational program.

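### The conditional three-group supportive analysis leaves Intervention patients who die or withdraw in no group but keeps such patients in Control, and its 25% trigger is counted over both arms

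*Protocol*

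**What the plan says.** Section 7.B.3.1 says that a secondary Per Protocol set, if judged necessary before database lock, would serve a supportive analysis of the primary criterion and a check of its robustness. It then gives an example. The analysis would be added "if it appears that 25.0% or more of the patients from the ITT data set have prematurely discontinued their allocated COPD management strategy" and still completed the study. It would compare average yearly unscheduled hospital days between three groups:

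- (i) "patients from the Intervention group having completed the study as planned";
- (ii) Intervention patients who stopped the programme early without being withdrawn from the study;
- (iii) Control patients, with no further condition.

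Section 3.D separates stopping the allocated strategy from leaving the study. Its reasons for study withdrawal are moving out of the centre's area, withdrawn consent and death. Section 4.B.5 gives the same kind of examples ("consent withdrawn, death"). The reasons in 3.D for stopping the strategy are a long-term move to a medicalised nursing home and non-compliance in general, which can apply to either arm. Its two specific non-compliance rules, on calls to the vocal server and on the home education sessions, are for the Intervention group only.

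Section 7.B makes everything apart from the primary analysis exploratory and descriptive and bars causal interpretation. The primary analysis in 7.B.3.5 is a Wilcoxon test on the whole ITT set.

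**The concern.** Groups (i) and (ii) both require that the patient was not withdrawn from the study; group (iii) does not. An Intervention patient who dies or leaves falls out of the comparison, and a Control patient with the same course stays in.

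The direction matters because of how the endpoint is built. Section 7.B.3.5 scales days to a year, so 18 hospital days in 182 days of follow-up count as 36. Section 1.C says that hospitalisations go with higher mortality. If withdrawn patients have more annualised hospital days than completers, they raise the Control average and are absent from the Intervention groups. The programme then looks better with no true effect.

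The groups also overlap as worded. The trigger describes stoppers who are followed to the end as having completed the study as planned, and almost the same words define group (i). Read literally, group (i) can contain group (ii).

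The trigger has a separate problem. It is meant to detect poor adherence to the programme but is counted over both arms, whereas the two specific discontinuation rules apply to Intervention only. Substantial programme drop-off could therefore go unexamined.

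**Working it through.** **1. The plan's own figures.** Section 7.B.2 assumes "an expected difference of 10 days of hospitalisation between the average individual yearly duration of unscheduled hospitalisation" and the other arm, "an estimated common standard deviation of 25 days", α = 0.05 ("two-sided conditions") and "power equal to 0.90".

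- Noether's formula for the rank-sum test is n = (z₀.₉₇₅ + z₀.₉₀)² / [6(P − 0.5)²], with P = Φ(10/(25√2)) = 0.6114.
- This gives n = 141.2, so 142 per arm, against 143 stated. The difference is minor; power at 143 is 0.903 by the same formula.
- 143/(1 − 0.0625) = 152.5, so 153 per arm and 306 in total, as stated.

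**2. Where each patient goes.**

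| Course | Intervention | Control |
|---|---|---|
| Completes study on allocated strategy | (i) | (iii) |
| Stops strategy, completes study | (ii); by its wording also (i) | (iii) |
| Dies, withdraws consent or moves away | none | (iii) |

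**3. How many.** The 306 planned patients are taken as the ITT set and the 25% yearly dropout as equal in both arms.

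- Withdrawn per arm: 0.25 × 153 = 38.25, about 38.
- Leaving before Visit 2 without primary data (at most 6.25%, section 7.B.2): 0.0625 × 153 = 9.6.
- Withdrawn with primary data: 38.25 − 9.56 = 28.7, about 29 per arm.

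So about 38 Intervention patients are in no group, of whom about 29 would have a usable value. About 29 Control withdrawals contribute theirs. The withdrawn share of Control is 28.7/(153 − 9.6) = 20% of those with data, or 25% if every withdrawal contributes.

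**4. Effect on the comparison of (i) with (iii) when the programme does nothing.** Let w be the withdrawn share of Control and g the excess annualised days of withdrawn patients over completers. Suppose group (i) has the completers' mean μ. The Control mean is (1 − w)μ + w(μ + g) = μ + wg, so the spurious difference is wg. The documents do not give g; the values below are assumptions.

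| Assumed g (days/year) | w = 20% | w = 25% |
|---|---|---|
| 0 | 0 | 0 |
| 10 | 2.0 | 2.5 |
| 20 | 4.0 | 5.0 |
| 40 | 8.0 | 10.0 |

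The planned effect is 10 days.

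**5. The trigger.** 0.25 × 306 = 76.5, so 77 patients who stop the strategy and complete the study. The Intervention share needed is (77 − Control stoppers)/153.

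| Controls who stop and complete | Intervention stoppers needed | Share of Intervention arm |
|---|---|---|
| 0 | 77 | 50.3% |
| 5% (8) | 69 | 45.1% |
| 10% (15) | 62 | 40.5% |
| 25% (38) | 39 | 25.5% |

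For example, 69 Intervention stoppers and no Control stoppers is 69/306 = 22.5%, which does not trigger although 45% of the arm stopped. Patients who stop the programme and later die or withdraw do not count towards the trigger at all.

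**The case against.** The strongest reply is that little hangs on this analysis. It is doubly conditional and introduced as an example, the data sets are to be fully defined before lock, section 7.B bars causal interpretation of anything but the primary test, and that test uses the whole ITT set. All of this stands and limits the consequence. It does not cure the asymmetry. The three groups are written out in the protocol, and 7.B.3.1 offers the comparison as an example of supportive analysis and robustness checking.

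A second reply is that the direction is not certain. Withdrawals include people who move away or withdraw consent, not only the sick. This also stands: with g = 0 the spurious difference is zero.

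A third is that Control patients can discontinue too, through nursing-home admission or general non-compliance. This is correct. A reader might infer that half of the Intervention arm must always stop before the analysis runs. The text supports that only if no Control discontinues.

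A reader might also infer that the Per Protocol set is biased in the same way, because section 7.B.3.4 lists "deviations in the allocation and/or the performance of the study educational program". That list names deviations to be evaluated. It is not a list of exclusions, and a deviation is major only if it is judged before lock likely to bias the efficacy results. The documents do not show a one-sided Per Protocol exclusion.

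**Conclusion.** The concern holds in limited form. As written, the three-group comparison drops Intervention deaths and withdrawals and keeps those in Control: about 38 of 153 patients in no group, against about 29 Control withdrawals with data, at the planned dropout. The omission follows from the text. The resulting bias depends on an excess in annualised hospital days that the documents do not give: about 2–2.5, 4–5 or 8–10 days for an assumed excess of 10, 20 or 40 days. The trigger corresponds to up to 50% of the Intervention arm if no Control discontinues, and to 45% or 40% if 5% or 10% of Controls do.

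A reader might go further and infer that the trial's main result is compromised, or that a particular false-positive rate follows. Neither is supported. The primary ITT test is untouched, section 7.B makes this analysis exploratory, the section names no test for it, and the documents give no mean hospital days or withdrawal-specific rates from which to derive such a rate.

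**What to change.** Change the wording of 7.B.3.1, and carry it into the analysis plan:

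- Make groups (i) and (ii) mutually exclusive and let them cover all Intervention ITT patients, by assigning those who died or withdrew according to their programme status at exit. Alternatively, apply the same withdrawal rule to Control.
- Count the 25% trigger within the Intervention group (39 of 153 at the planned size).
- State that the comparison of (i) with (iii) is not randomised and is not a robustness check of the primary result. This is still needed after regrouping, because group (i) remains selected on adherence and usual care has no matching selection.

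The cost is almost nothing. Section 3.D already has the reason, date and time of discontinuation and withdrawal recorded, so no new data are needed. The alternative rule would lose the roughly 29 Control withdrawals with data from this comparison, so assignment at exit is preferable.

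A complier-average estimate that treats programme completion as receipt is not a good substitute. Patients who stop have usually had part of the programme (home sessions before Visit 1, then telephone follow-up), so assignment could affect their outcome without completion.
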